9.1.1. Inclusion criteria

Patients must meet all of the following inclusion criteria to be eligible for inclusion in the study:

090177e19b7d94e0\Approved\Approved On: 29-Aug-2023 01:40 (GMT)

Apixaban

B0661183 NON-INTERVENTIONAL STUDY PROTOCOL

Protocol Version: 2.0 29 July 2022

1. Patients with ≥ 1 diagnosis code for VTE (inpatient [primary or secondary discharge diagnosis] or any position on an outpatient non-ancillary medical claim) between January 1, 2017 and October 31, 2021 (selection window).
 - Note: Qualifying outpatient encounters followed by qualifying inpatient encounters within 7 days will be considered an inpatient VTE event, unless LMWH or apixaban was initiated between encounters, in which case it will be classified as an outpatient VTE event
 - First date of claim with a VTE diagnosis code will be termed the ‘index VTE encounter’

2. Evidence of having active cancer, defined as ≥ 2 medical claims with a cancer diagnosis (excluding nonmelanoma skin cancer) on different days during the 6 months before or within 30-days after the index VTE event

OR

≥ 1 medical claim for a cancer diagnosis AND ≥ 1 claim for cancer treatment (eg: chemotherapy, radiation, immunotherapy, hormone therapy or cancer related surgery using national drug codes (NDC), international classification of diseases, tenth revision, clinical modification [ICD-10-CM] procedure codes or healthcare common procedure coding system [HCPCS] codes) during 6 months before or within 30 days after the index VTE encounter

3. ≥ 1 claim of apixaban or LMWH (dalteparin orenoxaparin) on or within 30 days following the index VTE encounter.
 - a. The date of the first apixaban or LMWH prescription fill will be designated as the index date
4. ≥ 12 months of continuous enrollment prior to the index date (pre-index)
5. ≥ 1 months of continuous enrollment including and following the index date (post-index)
 - a. Note: Each patient will have a variable follow-up period with a minimum of 1-month follow-up. Patients will be followed from the day after the index date through the earliest of the following: health plan disenrollment, index therapy discontinuation, switch to another anticoagulant, or study end (December 31, 2021).
 - b. Discontinuation will be defined as occurrence of a ≥ 30 day gap from the run-out of days’ supply of the index LMWH or apixaban prescription. The date of the discontinuation will be defined as the last day of the days’ supply of the last filled prescription.

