 - c. Switching will be defined as a prescription for an anticoagulant other than the index apixaban/LMWH prescription (unfractionated heparin, fondaparinux, other OAC, or LMWH for patients indexed on apixaban; unfractionated

PFIZER CONFIDENTIAL

CT24-WI-GL02-RF02 4.0 Non-Interventional Study Protocol Template For Secondary Data Collection Study 01-Jun-2022

Page 17 of 35

090177e19b7d94e0\Approved\Approved On: 29-Aug-2023 01:40 (GMT)

Apixaban**B0661183 NON-INTERVENTIONAL STUDY PROTOCOL**

Protocol Version: 2.0 29 July 2022

heparin, fondaparinux, or OAC (including apixaban) for patients indexed on LMWH) within 30 days following discontinuation of the index medication.

Note: Patients indexed on LMWH cohort will NOT be considered to have discontinued or switched if they change to an LMWH other than the index LMWH (dalteparin, enoxaparin, or tinzaparin)

6. ≥ 18 years of age at index

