9.3.1. Baseline Measures

Baseline demographic/clinical characteristics will be descriptively reported for the Apixaban and LMWH cohorts, both pre- and post-IPTW. Demographic characteristics will be measured as of the patient's index date while clinical characteristics will be measured over the 1-year pre-index baseline period.

Demographic Characteristics

- Age (mean, standard deviation [SD], median, interquartile range [IQR])
- Age group (18-24, 25-34, 35-44, 45-54, 55-64, 65-74, ≥ 75 years; n, %)
- Gender (male, female, unknown/missing; n, %)
- Geographic region (Northeast, Midwest, South, West, unknown/missing; n, %)
- Payer type (commercial, Medicaid, Medicare Risk, self-insured, other/unknown; n, %)
- Health plan type (consumer directed health care, health maintenance organization [HMO], indemnity, point-of-service [POS], preferred provider organization [PPO], other/unknown; n, %)

PFIZER CONFIDENTIAL

CT24-WI-GL02-RF02 4.0 Non-Interventional Study Protocol Template For Secondary Data Collection Study 01-Jun-2022

Page 19 of 35

090177e19b7d94e0\Approved\Approved On: 29-Aug-2023 01:40 (GMT)

Apixaban

B0661183 NON-INTERVENTIONAL STUDY PROTOCOL

Protocol Version: 2.0 29 July 2022

- Index date year (2017, 2018, 2019, 2020, 2021; n, %)
- Follow up duration in months (mean, SD, median, IQR)
 - Patients censored due to switching (n, %)
 - Patients censored due to discontinuation (n, %)

Clinical Characteristics

- Prescriber physician specialty (associated with the visit on or closest to the index date, as available) (n, %)
 - Primary care physician (PCP - general practice/family practice/internal medicine)
 - Cardiologist
 - Oncologist
 - Others
 - Unknown/missing
- Index VTE event setting (n, %)
 - Inpatient
 - Total inpatient cost of index VTE hospitalization (mean, SD, median)
 - Length of stay (LOS) of index hospitalization (mean, SD, median)
 - Outpatient
 - Note: Qualifying outpatient encounters followed by qualifying inpatient encounters within 7 days will be considered an inpatient VTE event, unless LMWH or apixaban was initiated between encounters, in which case it will be classified as an outpatient VTE event
- Index VTE type (n, %)
 - DVT
 - PE
 - DVT and PE
- Charlson Comorbidity Index (CCI, Dartmouth-Manitoba adaptation excluding cancer; continuous and categorical [0-1, 2, 3, 4+]) (n, %)
- NCI comorbidity index (continuous and categorical [0-1, 2, 3, 4+]) (n, %)
- Comorbidities of interest (ICD-10 diagnosis codes; n, %)

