9.3.2. All-cause HCRU and Costs Over the Post-Index Period (Post-IPTW)

All-cause HCRU and costs will be reported for the Apixaban and LMWH cohorts over the variable post-index period (minimum 1 month enrollment), post-IPTW. Costs will be reported

PFIZER CONFIDENTIAL

CT24-WI-GL02-RF02 4.0 Non-Interventional Study Protocol Template For Secondary Data Collection Study 01-Jun-2022

Page 23 of 35

090177e19b7d94e0\Approved\Approved On: 29-Aug-2023 01:40 (GMT)

Apixaban

B0661183 NON-INTERVENTIONAL STUDY PROTOCOL

Protocol Version: 2.0 29 July 2022

as per patient per month (PPPM). Over the post-index period, a 30 day period will be used (to represent a month) to ‘standardize’ the period of time for which costs and HCRU will be reported. For each patient, costs will be divided by the variable post-index period in total-person days and then multiplied by 30 to calculate PPPM costs. For example, if a patient has total costs of \$10,000 with 60 days of follow-up, the PPPM will be calculated as $(\$10,000/60) * 30 = \$5,000$.

HCRU will be expressed as both the proportion of patients with such utilization (e.g., the percentage of patients with at least one pharmacy claim, the percentage of patients with at least one physician office visits, etc.) as well as per-patient mean, SD, median and IQR number of visits/services. Costs will be expressed as per-patient mean, SD, median and IQR. Utilization and costs will be calculated on a per patient basis, averaged across the cohort. The denominator will include all patients in the cohort. Costs will be converted to 2021 US dollars (USD) using the medical component of the Consumer Price Index.

HCRU and costs will be reported for mutually exclusive categories: outpatient pharmacy, inpatient hospitalizations, and outpatient care. Outpatient care will comprise the following categories: ER visits, outpatient physician office visits, outpatient surgical visits, laboratory and pathology, radiology and all other services.

All-cause HCRU and costs will be reported for each of the following services:

- Pharmacy
 - Patients with ≥ 1 prescription fill (n, %)
 - Number of prescription fills per patient (mean, SD, median, IQR)
 - Total pharmacy cost per patient (mean, SD, median, IQR)
- Outpatient Services
 - Total outpatient medical care cost per patient (mean, SD, median, IQR)
 - Physician office visits
 - Patients with ≥ 1 physician office visit (n, %)
 - Number of physician office visits per patient (mean, SD, median, IQR)

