B0661183 NON-INTERVENTIONAL STUDY PROTOCOL

Protocol Version: 2.0 29 July 2022

9.3.3. Recurrent VTE, major bleeding, and CRNM bleeding related HCRU and costs in the post-index period

Recurrent VTE will be identified based on inpatient claims with VTE as the primary discharge diagnosis (ICD-10 diagnosis codes). If the admissions for recurrent VTE occur within 7 days of the index VTE event, irrespective of care setting, the events will not be considered as recurrent VTE events due to the proximity to the index VTE event and the index date.

Major bleeding will be defined by primary discharge diagnosis in the inpatient setting, including GI bleeding, intracranial hemorrhage (ICH), and other major bleeding.

CRNM bleeding will be defined as an inpatient encounter with a secondary diagnosis code for bleeding (without a major bleeding code in the primary position) or an outpatient encounter with a diagnosis code in any position for CRNM GI bleeding or other non-critical types of bleeding. **Error! Bookmark not defined. Error! Bookmark not defined.** Specifically, it is defined as:

- (1) An inpatient admission with a secondary diagnosis for “noncritical site” bleeding such as GI bleeding or other selected noncritical types/sites of bleeding (excluded if major bleeding occurred during the same hospitalization), OR
- (2) An outpatient encounter with a diagnosis code for GI bleeding and other selected noncritical types/sites of bleeding.

Any CRNM bleeding events (as described above) that follow a major bleeding event (described above) will not be included in the analysis of CRNM bleeding.

For the two therapy cohorts, the following outcomes related to recurrent VTE, major bleeding and CRNM will be reported post-IPTW.

- Recurrent VTE across the cohort
 - Patients with ≥ 1 such event (n, %)
 - Number of hospitalizations for VTE events (denoted by inpatient hospitalizations that meet the definition above) (mean, median, SD, IQR)
 - Time (in days) from index date to first recurrent VTE event (mean, median, SD, IQR)
- Major bleeding across the cohort
 - Patients with ≥ 1 such event (n, %)
 - Number of hospitalizations for major bleeding events (denoted by inpatient hospitalizations that meet the definition above) (mean, median, SD, IQR)
 - Time (in days) from index date to first major bleeding event (mean, median, SD, IQR)
- CRNM bleeding across the cohort
 - Patients with ≥ 1 such event (n, %)

PFIZER CONFIDENTIAL

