9.5. Study size

An earlier feasibility study estimated that there were 4,972 VTE patients with cancer with evidence of apixaban in PharMetrics® Plus. These counts were for informational purposes only and will not represent the actual number of patients to be utilized in the study. Application of other inclusion and exclusion criteria or other factors will reduce the sample size.

Sample size calculation was conducted to identify minimum number of patients in each cohort required for the analysis using the recurrent VTE event rates from Cohen et al.^{Error! Bookmark not defined.} and Agnelli et al.^{Error! Bookmark not defined.} to achieve a power of 80% at a 5% level of significance (two-sided). Using recurrent VTE rates 4.362% (148 recurrent VTE cases in 3,393 patients) in apixaban cohort and 6.483% (396 recurrent VTE cases in 6,108 patients) in LMWH cohort from Cohen et al., we require a minimum sample of 1,788 patients in each cohort to achieve 80% power. A minimum sample of 1,867 patients in each cohort is required to achieve 80% power at a 5% level of significance (two-sided) using recurrent VTE event rates from Agnelli et al. of 5.6% in apixaban cohort and 7.9% in dalteparin cohort. Based on the sample size calculations, for the current study we need a minimum sample in the range of 1,788-1,867 patients in each cohort.

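### Back-dating discontinuation to run-out, while keeping gaps under 30 days that end in a refill, makes an event in a supply gap count or vanish according to what is dispensed after it

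*Combined protocol and SAP*

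**What the plan says.** Item 5a of Section 9.1.1 sets when observation stops, with a change of drug and the close of the data as its last two criteria: "Patients will be followed from the day after the index date through the earliest of the following: health plan disenrollment, index therapy discontinuation, switch to". Item 5b sets the condition for discontinuation: "Discontinuation will be defined as occurrence of a ≥ 30 day gap from the run-out of" supply. It then sets the date: "The date of the discontinuation will be defined as the last day of the" supply of the final fill. The condition therefore looks 30 days ahead, and the date goes back to day 0 of the gap.

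A gap shorter than 30 days that ends in a refill is not discontinuation. No text removes its days, costs or events, so their retention is implied by 5a and 5b rather than stated.

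Item 5c defines switching as a different anticoagulant "within 30 days following discontinuation of the index medication". Sections 9.1 and 9.1.1 nevertheless list switching as an end-of-follow-up reason of its own, and Section 9.3.1 counts patients censored for switching separately from those censored for discontinuation.

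Outcomes are defined by claims alone. In Section 9.3.3, for example, "Recurrent VTE will be identified based on inpatient claims with VTE as the primary discharge diagnosis"; there is no rule for events in a supply gap. In Section 9.3.2, "costs will be divided by the variable post-index period in total-person days and then multiplied by 30 to calculate PPPM costs", so the end date sets both numerator and denominator. Section 9.7 has no grace period, alternative end date, weighting for censoring or sensitivity analysis, and Section 9.9 does not mention the point.

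**The concern.** Whether an outcome counts is decided by a fill made after that outcome. A recurrent VTE or a bleed is a plausible reason not to refill the index drug, so the events most likely to end index treatment are also those most likely to be deleted. Stabilized IPTW balances covariates measured at baseline and cannot undo selection on a later fill.

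Both primary objectives are cost comparisons. Event-related costs rest on few non-zero patients; Section 9.7 chooses two-part models for that reason. If the cohorts differ in how often patients resume the index drug after a gap event, the event, HCRU and cost comparisons can differ even when true risk is equal. The protocol leaves room for this: a change from one LMWH to another is neither a discontinuation nor a switch, whereas an apixaban patient who moves to another product has left the index drug.

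**Working it through.** **The plan's own figure.** No number is given for the discontinuation rule. The sample size does reproduce. With 5.6% vs 7.9%, two-sided 5%, 80% power and n = [1.960·√(2p̄q̄) + 0.842·√(p₁q₁+p₂q₂)]² / (p₁−p₂)², p̄ = 0.0675: (0.6954 + 0.2983)² / 0.023² = 1,867 per cohort. The second calculation gives 1,789 against the stated 1,788. Neither is disputed.

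**One event under the written rules.** Assume supply ends on day 60 and a $20,000 recurrent VTE admission occurs on day 70.

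| What is dispensed afterwards | Follow-up ends | Event-related PPPM cost |
|---|---|---|
| Index drug on day 80, supply to day 109, then stops | day 109 | 20,000/109 × 30 = $5,505 |
| Nothing for at least 30 days | day 60 | $0 |
| Another anticoagulant on day 75, 5b and 5c read literally | day 60 | $0 |
| Another anticoagulant on day 75, switch censored at its fill | day 75 | 20,000/75 × 30 = $8,000 |

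The event is the same in all four rows. The last two rows differ only in how the switch date is read.

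**How large it could be.** Every input here is assumed; none is in the documents. Fills last 30 days. A patient stops after each fill with probability s = 0.15, 0.25 or 0.40. Refilled gaps last 0 to 14 days (mean 7). Event risk in a gap is k = 1 or 2 times the on-supply risk. After a gap event the index drug is resumed within 30 days with probability r. True risk and stopping are equal in both cohorts, and events are rare.

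- On-supply days S = 30/s; refilled-gap days R = 7(1/s − 1); final window 30 days.
- Share of events falling in gaps: G = k(R+30) / [S + k(R+30)].
- Share dropped by the current rule: (1 − r)G.
- Apparent rate ratio: [1 − (1−r₁)G] / [1 − (1−r₂)G].

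| s | S | R | G, k = 1 | G, k = 2 |
|---|---|---|---|---|
| 0.15 | 200 | 39.7 | 69.7/269.7 = 0.258 | 139.3/339.3 = 0.411 |
| 0.25 | 120 | 21.0 | 51/171 = 0.298 | 102/222 = 0.459 |
| 0.40 | 75 | 10.5 | 40.5/115.5 = 0.351 | 81/156 = 0.519 |

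Example, s = 0.15, k = 1, r = 0.3 vs 0.7: (1 − 0.7×0.258)/(1 − 0.3×0.258) = 0.819/0.923 = 0.89.

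| r₁ vs r₂ | Ratio, k = 1 | Ratio, k = 2 |
|---|---|---|
| 0.5 vs 0.5 | 1.00 | 1.00 |
| 0.45 vs 0.55 | 0.96–0.97 | 0.93–0.95 |
| 0.4 vs 0.6 | 0.92–0.94 | 0.87–0.90 |
| 0.3 vs 0.7 | 0.84–0.89 | 0.75–0.81 |

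Simulations of this kind of model gave about 0.89–0.94 for 0.4 vs 0.6 and 0.75–0.89 for 0.3 vs 0.7. Exchanging the cohorts inverts the ratios: 0.75 becomes 1/0.75 = 1.33. Counting events to run-out plus 30 days for everyone returned about 0.98–1.03.

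**Loss without any difference between cohorts.** Power = Φ{[√n·|p₁−p₂| − 1.960·√(2p̄q̄)] / √(p₁q₁+p₂q₂)} with n = 1,867. If 10, 20 or 30% of events are dropped equally from 5.6% and 7.9%, power falls from 80.0% to 75.4, 70.1 or 64.0%. For 10%: (0.8944 − 0.6621)/0.3375 = 0.688, and Φ(0.688) = 0.754.

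**What a 30-day window adds.** Mean follow-up rises by 30/(S+R): 30/239.7 = 12.5%, 30/141 = 21.3%, 30/85.5 = 35.1%. If one cohort stops at 0.15 per fill and the other at 0.40, the on-supply share of follow-up is now 200/239.7 = 0.83 vs 75/85.5 = 0.88 (ratio 0.95). Under the window it is 200/269.7 = 0.74 vs 75/115.5 = 0.65 (ratio 1.14).

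**The case against.** Ending follow-up at run-out confines it to supplied days for patients who stop, which is a recognised on-treatment convention. That stands as far as it goes. But off-supply days of patients who refill are kept, so the rule is not consistently on-treatment.

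A reader might infer that the comparison is biased by a known amount, or towards a known drug. The documents do not support that. The ratios follow directly from assumed resumption probabilities, vanish when these are equal, and invert if the cohorts are exchanged. The LMWH-to-LMWH note defines continuation within a class; it says nothing about how often patients resume. The ratios also describe event rates, not the primary all-cause PPPM cost, for which no effect has been shown.

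A reader might also infer that the protocol plainly deletes gap events in switchers. Read literally, 5b and 5c do cut a switcher at run-out, but the switch criterion could then never be the earliest one, although the protocol lists it and tabulates it. This is an unresolved contradiction, not a settled rule.

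A fixed window has real costs. It dilutes index-drug cost more in the cohort that stops sooner, so making it the main rule for all-cause cost is a trade-off. Nor does it isolate on-drug risk. With k = 2 and stopping at 0.15 vs 0.40, event rates relative to the on-drug rate are 339.3/269.7 = 1.26 and 156/115.5 = 1.35, a ratio of 0.93 despite equal on-drug risk. These objections stand and limit the fix.

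Run-outs fewer than 30 days before 31 December 2021 cannot meet the gap criterion. That is administrative, has no stated size, and is not relied on here.

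**Conclusion.** The defect holds as a matter of the written rules: for patients with no other anticoagulant, a gap event and its cost are kept or dropped according to a later index-drug fill. For switchers the same follows on the literal reading, but the passages conflict. It is outcome-dependent censoring that baseline IPTW cannot correct, and nothing elsewhere in the plan mitigates it. That short refilled gaps remain in follow-up is implied, not stated.

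Size and direction cannot be derived from the documents. Across the assumed patterns the ratio runs from 1.0 down to about 0.75, or up to its inverse, and should be read as sensitivity only. The point justifies a uniform window for event outcomes and a sensitivity analysis for all-cause outcomes. It does not justify replacing the main rule for all-cause cost.

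**What to change.** 1. For recurrent VTE, major bleeding and CRNM bleeding, and their related HCRU and costs, end follow-up for every patient at the earliest of run-out plus 30 days (the protocol's own gap), the fill date of another anticoagulant, disenrollment or study end. Count events, costs and days to that date whatever is filled later. Report censoring at run-out as a sensitivity analysis.
2. For all-cause PPPM cost and HCRU, keep the current rule and prespecify the run-out plus 30-day rule as a sensitivity analysis.
3. State in 5c that switchers are censored at the switch fill date, and bring Sections 9.1, 9.1.1 and 9.3.1 into line.

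The change needs a few sentences in 5a to 5c, a second end-date variable and extra table columns, with no new data. The price is that off-supply days enter event follow-up: about 12 to 35% more mean follow-up under the assumed stopping rates, and more in the cohort that stops sooner. The event comparison then describes risk on treatment plus 30 days and should be labelled so. Costs after a switch fill are still not captured, while later costs of patients who resume are. Excluding off-supply days for everyone would also be consistent and could be a further sensitivity analysis, but it discards all gap events.

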9.1.2. Exclusion criteria

Patients meeting any of the following criteria will be excluded from the study:

1. ≥ 1 claim with a ICD-10 diagnosis code of atrial fibrillation/flutter during the 12-month pre-index
2. ≥ 1 claim with a ICD-10 procedure code of mechanical heart valve during the 12-month pre-index
3. ≥ 1 claim with a ICD-10 diagnosis code of VTE diagnosis during the 12-month prior to index VTE encounter
4. ≥ 1 prescription claim of OAC or parenteral anticoagulant (PAC) (unless prophylactic) before the index VTE encounter
 - a. The OAC or PAC prescription claim will be considered prophylactic if duration of the prescription is ≤ 42 days AND the start date of OAC or PAC occurs within 2 days before or 7 days after knee/hip replacement surgery
OR
Start date of OAC or PAC occurred within 7 days after the admission of an hospitalization associated with 'medically ill' (primary discharge diagnosis; codes provided separately) AND with a ≥ 3 -day length of stay of the hospitalization
5. ≥ 1 claim with a ICD-10 procedure code or Common Procedural Terminology (CPT) code of inferior vena cava filter during the study period
6. ≥ 1 claim with a ICD-10 diagnosis code of antiphospholipid syndrome (APS) during the study period
7. ≥ 1 claim with a ICD-10 diagnosis code or procedure code (ICD-10 or HCPCS codes) of pregnancy during the study period
8. ≥ 1 prescription claim of an anticoagulant other than index apixaban or LMWH treatment between the index VTE encounter and index date. Other anticoagulants include heparin, fondaparinux, warfarin, dabigatran, rivaroxaban, and edoxaban
9. Data quality issues (with Medicare Cost coverage or State Children's Health Insurance Program (SCHIP), invalid year of birth or health plan enrollment dates) ('missing' will be reported for gender and region)

PFIZER CONFIDENTIAL

CT24-WI-GL02-RF02 4.0 Non-Interventional Study Protocol Template For Secondary Data Collection Study 01-Jun-2022

Page 18 of 35

090177e19b7d94e0\Approved\Approved On: 29-Aug-2023 01:40 (GMT)

Apixaban**B0661183 NON-INTERVENTIONAL STUDY PROTOCOL**

Protocol Version: 2.0 29 July 2022

A preliminary attrition table will be provided to Pfizer/Bristol Myers Squibb (BMS) for review, at which time modifications to the inclusion and exclusion criteria may be implemented.

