9.1. Study period and study design

The analysis will be conducted using data from 01 January 2016 through 31 December 2021 or the latest available data at the time of extraction (i.e., the *study period*). Patients will be identified during a *selection window* of 01 January 2017 to 31 October 2021. The date of the first apixaban or LMWH prescription on or within the 30 days following a VTE diagnosis will be termed as the index date. Patients will be required to have continuous enrollment with medical and pharmacy benefits for 12-months prior to the index date to assess study eligibility criteria and to measure baseline characteristics (*the baseline or pre-index period*). Patients will also be required to have continuous enrollment with medical and pharmacy benefits for at least one month (30 days) starting on and following the index date (the follow-up or post-index period) and will be followed through the earliest of the following: health plan disenrollment, index therapy discontinuation, switch to another anticoagulant (includes switch to the other study medication or unfractionated heparin, fondaparinux, warfarin, rivaroxaban, dabigatran, or edoxaban), or end of study period (31 December 2021).

Note: Patients in the LMWH cohort will NOT be considered to have discontinued or switched if they change to an LMWH other than the index LMWH (dalteparin, enoxaparin, or tinzaparin).

Figure 1. Study Period

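### Exclusions 5 to 7 run to the end of the study period, so cohort entry depends on post-index codes; for vena cava filters this may remove patients with on-treatment events and all their costs

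*Combined protocol and SAP*

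**What the plan says.** Section 9.1.2 gives three exclusions the same long window:

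- exclusion 5, a procedure code or "CPT) code of inferior vena cava filter during the study period";
- exclusion 6, a "diagnosis code of antiphospholipid syndrome (APS) during the study period";
- exclusion 7, a diagnosis or procedure code "of pregnancy during the study period".

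Section 9.1 defines that period as "data from 01 January 2016 through 31 December 2021 or the latest available data at the time of extraction". Patients enter earlier than its end: "Patients will be identified during a *selection window* of 01 January 2017 to 31 October 2021".

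The neighbouring exclusions are bounded differently. Exclusion 1 uses a "diagnosis code of atrial fibrillation/flutter during the 12-month pre-index" period and exclusion 2 a "procedure code of mechanical heart valve during the 12-month pre-index" period. Exclusions 3 and 4 look back from the index VTE encounter. Exclusion 8 covers the interval between that encounter and the index date. Section 9.1 also names the 12 months before index as the period in which eligibility is assessed. No reason is given for the longer window in exclusions 5 to 7, and the abstract lists these conditions with no window at all.

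**The concern.** An exclusion that can be triggered after index makes membership of the cohort depend on what happens during or after treatment. The primary objectives in section 8 are all-cause costs and the costs of recurrent VTE, major bleeding and clinically relevant non-major bleeding.

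A filter coded after index is a plausible consequence of a bleed that interrupts anticoagulation or of a recurrence on treatment. Work-up after a recurrence could, less directly, yield an APS code. Such a patient is not censored. The whole record is dropped, including the event and every cost before and after it. For pregnancy there is no comparable link to the outcomes, and the objection is only that eligibility uses future data.

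The stabilised weights in sections 9.3 and 9.7 are built to balance baseline characteristics among the patients who remain. They cannot restore patients removed because of later events. Section 9.9 does not list this selection as a limitation, and section 9.7 plans no sensitivity analysis for it.

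**Working it through.** **1. How far the windows reach past index.** The last qualifying VTE date is 31 October 2021 and the first is 1 January 2017. To 31 December 2021 that leaves 61 days at the short end and 1,825 days at the long end. The index date can fall up to 30 days after the VTE encounter, so at least 61 − 30 = 31 days of the exclusion window lie after index for every patient. For the earliest patients it is close to five years. The window can also outlast a patient's own follow-up, which stops at discontinuation or switch (sections 9.1 and 9.1.1). A code recorded after costing has ended still removes the patient.

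**2. The plan's own figure.** Section 9.5 sizes the study on recurrent VTE, with p₁ = 148/3,393 = 0.043619 (apixaban) and p₂ = 396/6,108 = 0.064833 (LMWH), two-sided 5% and 80% power.

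n = [1.960·√(2p̄(1−p̄)) + 0.8416·√(p₁(1−p₁) + p₂(1−p₂))]² / (p₂−p₁)², with p̄ = 0.054226

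= [0.6277 + 0.2692]² / 0.0212138² = 1,788 per cohort.

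The same formula with 5.6% and 7.9% gives 1,867. Both stated minimums reproduce and are not in dispute.

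**3. Illustration of the effect on event rates.** The documents give no frequency, timing, reason or cost for post-index filter, APS or pregnancy codes. The removal fraction f below is therefore an assumption, shown over a range. If a fraction f of patients with the event is removed and no one else is, the observed rate is

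e′ = e(1−f) / (1−e·f).

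For example, with f = 0.10: 0.04362 × 0.90 / (1 − 0.004362) = 3.94%, and 0.06483 × 0.90 / (1 − 0.006483) = 5.87%.

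| f apixaban | f LMWH | Apixaban | LMWH | Difference (points) | Risk ratio |
|---|---|---|---|---|---|
| 0 | 0 | 4.36% | 6.48% | 2.12 | 0.67 |
| 10% | 10% | 3.94% | 5.87% | 1.93 | 0.67 |
| 20% | 20% | 3.52% | 5.25% | 1.73 | 0.67 |
| 30% | 30% | 3.09% | 4.63% | 1.53 | 0.67 |
| 10% | 20% | 3.94% | 5.25% | 1.31 | 0.75 |
| 20% | 10% | 3.52% | 5.87% | 2.35 | 0.60 |

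Equal removal lowers both rates and the absolute gap but leaves the ratio almost unchanged. Unequal removal moves the ratio in either direction.

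**4. What this does not measure.** The table concerns recurrent-VTE proportions. The primary outcomes are costs, and no cost input is available from which to compute the effect on them.

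**The case against.** Several points on the other side are fair.

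- *The three exclusions are not alike.* A reader might infer that all of them remove patients because of bleeding or recurrence. The documents do not support that. The pathway is credible mainly for filters, weaker for APS and absent for pregnancy.
- *Some of the excluded codes are unobjectionable.* A code before or at index is legitimate baseline information, and a filter soon after index may belong to the care of the index VTE. The documents do not allow these to be apportioned.
- *A reader might infer that the costliest outcomes are removed.* No cost for such patients is given. Nor does an associated admission set the excluded events apart: section 9.3.3 defines every recurrent VTE and every major bleed as an inpatient event, so retained events include an admission too.
- *A reader might infer that a true difference is shrunk.* With equal removal that is so only on the absolute scale. The example model in section 9.7 estimates a cost ratio, though weighted mean comparisons are planned as well. With unequal removal the contrast can widen.
- *Other criteria look past index.* The 30-day enrolment requirement does. But it is short, the same length for everyone, and acknowledged in section 9.9.
- *The criteria may change after attrition review.* Section 9.1.2 allows this, but the clause does not mention these windows and commits to nothing.

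These points limit what can be claimed about size and direction. None of them answers the central fact that the exclusion windows extend past index without a stated reason.

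**Conclusion.** The defect is established from the text: exclusions 5 to 7 condition cohort entry on post-index information, unlike exclusions 1 to 4 and 8. For filters in particular, and less directly for APS, this may selectively remove patients with on-treatment bleeding or recurrence, with all their costs, from the primary comparisons. Event rates and costs may be understated in both cohorts.

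Neither the size nor the between-cohort direction of the bias can be determined from the documents. The illustrative figures rest entirely on assumed removal fractions and on no removal of event-free patients. Claims that the costliest outcomes are lost, or that the comparison is pulled towards no difference, go beyond the evidence. A bias of unknown sign in the primary comparison, which weighting cannot repair and an edit to the criteria can avoid, is still reason enough to change the plan.

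**What to change.** In exclusions 5, 6 and 7, replace the study-period window with *in all available data up to and including the index date*. This ends the forward look while keeping the long look-back. Cutting the window to 12 months before index would needlessly admit, for example, a patient indexed in 2020 with a filter or APS code from 2016.

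Retain patients with later codes and count their costs within the follow-up already defined, which ends at discontinuation, switch, disenrolment or study end. Costs after that point remain uncounted, as for everyone else. In the attrition table, report by cohort how many patients the post-index codes would have removed. The current rule can be kept as a sensitivity analysis.

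The cost is three wording changes, a rerun of the attrition table (with weights and models refitted if they have already been run), and a few later-coded patients retained. No new data are needed, and the 1,788 to 1,867 minimum per cohort does not change.
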